11.1.3 Severity of AEs

11.1.3.1 Identify the AE using the CTCAE version 4.0. The CTCAE provides descriptive terminology (MedDRA lowest level term) and a grading scale for each AE listed. A copy of the CTCAE can be found at http://ctep.cancer.gov/protocolDevelopment/electronic_applications/ctc.htm

AEs will be assessed according to the grade associated with the CTCAE term. AEs that do not have a corresponding CTCAE term will be assessed according to the general guidelines for grading used in the CTCAE v4.0 as stated below.

CTCAE v4.0 general severity guidelines:

Grade	Severity	Description
1	Mild	Mild; asymptomatic or mild symptoms; clinical or diagnostic observations only; intervention not indicated.
2	Moderate	Moderate; minimal, local or noninvasive intervention indicated; limiting age-appropriate instrumental activities of daily living (ADL)*.
3	Severe	Severe or medically significant but not immediately life-threatening; hospitalization or prolongation of hospitalization indicated; disabling; limiting self-care ADL**.
4	Life-threatening	Life-threatening consequences; urgent intervention indicated.
5	Fatal	Death related to AE.

ADL

*Instrumental ADL refers to preparing meals, shopping for groceries or clothes, using the telephone, managing money, *etc.*

**Self-care ADL refers to bathing, dressing and undressing, feeding self, using the toilet, taking medications, and not bedridden.

11.1.4 Assessment of relationship of AE to treatment

The possibility that the adverse event is related to study agent will be classified as one of the following: not related, unlikely, possible, probable, definite.

11.1.5 Follow-up of AEs

All AEs, including lab abnormalities that in the opinion of the investigator are clinically significant, will be followed according to good medical practices and documented as such. AEs with a “possibly”, “probably” or “definitely” attribution to study agent will be monitored up to 20-30 days after surgery via phone call.

11.2 Serious Adverse Events

11.2.1 DEFINITION: Regulations at 21 CFR §312.32 (revised April 1, 2014) defines an SAE as any untoward medical occurrence that at any dose has one or more of the following outcomes:

- Death
- A life-threatening AE
- Inpatient hospitalization or prolongation of existing hospitalization
- A persistent or significant incapacity or substantial disruption of the ability to conduct normal life functions
- A congenital anomaly or birth defect
- Important medical events that may not be immediately life-threatening or result in death or hospitalization should also be considered serious when, based upon appropriate medical judgment, they may jeopardize the patient and may require medical or surgical intervention to prevent one of the other outcomes.

11.2.2 Reporting SAEs to DCP

The organization that experiences the serious adverse event (SAE) should report the SAE to the following 3 entities: 1) NCI DCP, 2) DCP's regulatory contractor CCSA, and 3) MDACC, the CLO. Detailed reporting instructions are provided below. In addition, all participating organizations will follow their IRB requirements for SAE reporting.

11.2.2.1 The Lead Organization and all Participating Organizations will report SAEs on the DCP SAE Report Form found at <http://prevention.cancer.gov/clinical-trials/clinical-trials-management/protocol-information-office/pio-instructions-and-tools/2012-consortia>.

11.2.2.2 Reporting within 24 hours of knowledge of the event.

11.2.2.2(A) Report to the NCI DCP Medical Monitor within 24 hours:
Contact the DCP Medical Monitor by phone within 24 hours of knowledge of the event.

[name]
NCI/Division of Cancer Prevention
[name]
[name]
[contact]
[contact]
Email: [contact]

Include the following information when calling the Medical Monitor:

- Date and time of the SAE
- Date and time of the SAE report
- Name of reporter
- Call back phone number
- Affiliation/Institution conducting the study
- DCP protocol number
- Title of protocol
- Description of the SAE, including attribution to drug and expectedness

11.2.2.2(B) Report to the Consortium Lead Organization (CLO) PI ([name]) within 24 hours of knowledge of the event:
Report all SAEs to the Consortium Lead Organization PI ([name]) within 24 hours of knowledge of the event. The same information reported to the DCP Medical Monitor should be provided to the CLO Coordinator via email, phone or fax within 24 hours of knowledge of the event.

11.2.2.3 Reporting within 48 hours of knowledge of the event:

11.2.2.3 (A) Email the written SAE reports to the DCP Medical Monitor within 48 hours of learning of the event using the paper SAE form. The SAE forms should be obtained at <http://prevention.cancer.gov/clinical-trials/clinical-trials-management/protocol-information-office/pio-instructions-and-tools/2012-consortia>.

11.2.2.3 (B) The written SAE reports will also be emailed to DCP's Regulatory Contractor, CCS Associates, at [contact].

11.2.2.3 (C) The written SAE report will also be faxed to the Consortium Lead Organization PI ([name]), at [contact] or emailed at [contact].

It is the responsibility of the CLO to inform the Lead Protocol PI upon receipt of the report from the organization experiencing the event.

11.2.2.4 The DCP Medical Monitor and regulatory staff will determine which SAEs require FDA submission.

11.2.2.5 The Lead Organization and all Participating Organizations will comply with applicable regulatory requirements related to reporting SAEs to the IRB/IEC.

11.2.2.6 Follow-up of SAE

Site staff should send follow-up reports as requested when additional information is available. Additional information should be entered on the DCP SAE form in the appropriate format. Follow-up information should be sent to DCP as soon as available. SAEs will be monitored up to 30 days after post-treatment with a visit or a phone call based on the severity of the SAE

12. STUDY MONITORING

12.1 Data Management

This study will report clinical data using the Data Management Initiative (DMI) web-based application managed by the Consortium Biostatistics and Data Management Core. Data Management Initiative (DMI) infrastructure has been developed in the Division of Quantitative Sciences (DQS), MD Anderson Cancer Center. This infrastructure supplies integrated database and software services for web-based data collection, randomized treatment assignment, reporting, query, data download, and data quality management. The DMI will be the database of record for the protocol and subject to NCI and FDA audit. All DMI users will be trained to use the DMI system and will comply with the instructions in the protocol-specific "DMI User Manual" as well as applicable regulatory requirements such as 21 CFR; Part 11. Data management procedures for this protocol will adhere to the Data Management Plan (DMP) on file at the DCP for contract HHSN261201200034I.

12.2 Case Report Forms

Participant data will be collected using protocol-specific case report forms (CRF) developed from the standard set of DCP Chemoprevention CRF Templates and utilizing NCI-approved Common Data Elements (CDEs). The approved CRFs will be used to create the electronic CRF (e-CRF) screens in the DMI application. Site staff will enter data into the e-CRF. Amended CRFs will be submitted to the DCP Protocol Information Office for review and approval. Approved changes will be programmed into the DMI database by the Consortium Biostatistics and Data Management Core.

12.3 Source Documents

Source documentation will include only those documents containing original forms of data, including clinic charts, shadow files, hospital charts, and physician notes. Data recorded directly on the CRFs designated as source documents (i.e., no prior written or electronic record of data) will be considered source data. All other data recorded on the CRFs will not be considered source documentation.

12.4 Data and Safety Monitoring Plan

The Data and Safety Monitoring Plan for the MD Anderson Consortium is on file at the DCP. This study will be monitored by the MDACC Data and Safety Monitoring Board, the data and safety monitoring board of record for this study. The Data Safety and Monitoring Board (DSMB) reports to the President, or his designee, as the on-campus representative of The University of Texas Board of Regents. It oversees the data and patient safety issues for randomized clinical trials that originate at MD Anderson; that are coordinated or analyzed by MD Anderson and are not being monitored by any other DSMB; or have been designated as requiring DSMB monitoring at the request of the IRB, the CRC, or institution. The primary objectives of the DSMB are to ensure that patients' rights pertaining to participation in a research study are protected, and that patients' interests are prioritized over the interests of the scientific investigation. Responsibilities include:

- (a) Review interim analyses of outcome data (prepared by the study statistician or other responsible person at the time points defined in the study) approved by the IRB and additional time points as determined by the DSMB, and to recommend, if necessary, whether the study needs to be changed or terminated based on these analyses;
- (b) Determine whether, and to whom, outcome results should be released prior to the reporting of study results;
- (c) Review interim toxicity data and efficacy of treatment;
- (d) Review major research modifications proposed by the investigator or appropriate study committee prior to implementation (e.g., termination, dropping an arm based on toxicity results from the study or results of other studies, increasing target sample size).

Refer to the Data and Safety Monitoring Plan for the MD Anderson Consortium on file at the DCP for further details.

12.5 Sponsor or FDA Monitoring

The NCI, DCP (or their designee), pharmaceutical collaborator (or their designee), or FDA may monitor/audit various aspects of the study. These monitors will be given access to facilities, databases, supplies and records to review and verify data pertinent to the study.

12.6 Record Retention

Clinical records for all participants, including CRFs, all source documentation (containing evidence to study eligibility, history and physical findings, laboratory data, results of consultations, *etc.*), as well as IRB records and other regulatory documentation will be retained by the Investigator in a secure storage facility in compliance with Health Insurance Portability and Accountability Act (HIPAA), Office of Human Research Protections (OHRP), Food and Drug Administration (FDA) regulations and guidances, and NCI/DCP requirements, unless the standard at the site is more stringent. For NCI/DCP, records will be retained for at least three years after the completion of the research. NCI will be notified prior to the planned destruction of any materials. The records should be accessible for inspection and copying by authorized persons of the Food and Drug Administration, the Italian Ministry of Health representative and Italian Agency of Drug (AIFA). If the study is done outside of the United States, applicable regulatory requirements for the specific country participating in the study also apply.

12.7 Cooperative Research and Development Agreement (CRADA)/Clinical Trials Agreement (CTA)

N/A

13. STATISTICAL CONSIDERATIONS

13.1 Study Design/Description

The trial is a randomized, double-blind, non-inferiority phase IIb study. Participants will be randomized to receive exemestane as one dose of 25 mg once a day; or 25 mg three times a week; or 25 mg once a week for at least four up to six weeks. Analysis will be performed according to intention to treat principle and then according to efficacy.

13.2 Randomization/Stratification

In order to keep at minimum the imbalance in treatments a stratified blocked randomization strategy will be used considering only the relevant prognostic factors. Participants will be stratified according to center and BMI (<25 kg/m² versus ≥ 25 kg/m²). Subjects with a BMI <25 kg/m² will be limited to 50% per site. A fixed block randomization will be carried out with a block size of 6 patients.

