1. OBJECTIVES

1.1 Primary Objective

It has been shown that exemestane reduces estradiol levels both at the standard dose (25 mg/day) and at lower doses. We expect to achieve with 25 mg three times a week and 25 mg/week similar effects in estradiol reductions to the standard dose of 25 mg daily.

Non-inferiority of percent change in time of serum estradiol levels, adjusted for baseline levels, following four up to six weeks of exemestane 25 mg given three times per week or one time per week compared with exemestane 25 mg daily dosing.

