4.4 Recruitment and Retention Plan

This multicenter protocol will be conducted at the following five sites: the European Institute of Oncology (IEO), Milan, Italy; the E.O. Galliera, Genoa, Italy; the Columbia University Medical Center (CUMC), New York, NY; the UT MD Anderson Cancer Center, Houston, TX; and the Moffitt Cancer Center, University of South Florida, Tampa, FL. The IEO will be the Lead Site. The high rate of breast cancer surgeries at these sites will allow the recruitment of the required samples size. Efforts will be made to enroll women from a diversity of ethnic and socio-economic backgrounds. Recruitment and retention effort will be evaluated routinely by the site coordinator and the study staff. The study recruitment and retention plan will be modified as necessary to promote rapid accrual and to assure 100% recruitment rate of participants. Please refer to the study-specific recruitment and retention plan for more details.

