13.4 Primary Objective, Endpoint(s), Analysis Plan

Primary objective and primary endpoint

Since the primary objective of this study is to assess if the reduction in estradiol with the standard dose is comparable with the other lower doses, we will measure the estradiol before and after treatment. Thus, the primary endpoint is the percentage change of serum estradiol concentration from baseline and we will compare the median change and percentage changes among arms.

We choose the percentage change as the primary endpoint because it will improve generalization of results, given the wide variability among different assays, and because we predict that a large percentage of participants will have the final values of estradiol below the detectable level.

Analysis plan

We will present full distribution and median values of estradiol at baseline (before treatment), at post (after treatment), and changes and percentage changes (with interquartile ranges) of estradiol level, from baseline to post, by arms. Differences by arms of % change, change and final values will be tested considering t-test and ANCOVA models. Estradiol at baseline will be included as explanatory variable together with other possible confounders such as BMI, age and time since last dose. Normal distribution of residuals from full model will be checked and, if needed, a transformation will be considered.

We will also compare percentages of participants with final values of estradiol below the detectable level by arms with Chi-square tests and logistic models.

We will carry out the two comparisons with the standard dose considering $\alpha=0.025$.

Power analysis

Given the expected reduction of at least 80% change with exemestane at 25 mg daily (56) considered as reference group (control arm) against 25 mg 3 times a week, or 25 mg weekly, for the power calculation we assume a non-inferiority difference of 6% in percentage changes of estradiol after treatment from baseline, using a one-sided, two-sample t-test. A total sample size of 162 participants (54 participants per arm), enables us to achieve 80% power with a margin of equivalence of -6% in the mean percentage changes from baseline at the lower dose compared to the standard dose. The true difference between the means percentage changes is assumed to be 0.0%.

The significance level of the test is 0.025 to take into account of multiple comparisons (we will compare the changes at the two low doses with the standard dose)(57).

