- Adipokines: change in leptin and adiponectin serum concentrations will be analyzed and compared among the different treatments arms. These measurements will be performed by the use of commercially available enzyme linked immunoassays purchased from R&D systems (SPACE Import-Export Srl, Milan, Italy).
- Measurement of breast estradiol concentration in tumor and normal breast tissue at time of surgery.
- Centralized evaluation of ER, PgR, Her2 expression in tumor comparing pre-treatment levels (tru-cut biopsy) to post-treatment level expression (surgical specimen). Centralized evaluation of Ki-67 in adjacent intraepithelial neoplasia and or grossly benign tissue.
- Drug measurements of exemestane and 17-dihydroxyexemestane on frozen tissue samples, when available.
- Proteomic analysis will be performed with the new Fusion Tribrid mass spectrometer in [name] Shared Resource for the Herbert Irving Comprehensive Cancer Center (HICCC) at CUMC.
- To analyze the UGT2B17 gene we will use Taqman copy number variation assay (Life Technologies, Monza, Italy).
- Crown like structures in mammary fat tissue by IHC (CD68), comparing pre-treatment (tru-cut biopsy) versus post-treatment (surgical specimens).

Analysis plan

We will present full distributions and median values of circulating biomarkers, Ki-67, exemestane and 17-dihydroxyexemestane in tissue at baseline, after treatment and also of changes and percentage changes (with interquartile ranges) of all continuous variable, by arms. ANCOVA models will evaluate the associations of post values (after treatment) and changes from baseline by study arms adjusting for baseline values, explanatory variables and possible confounders (such as age and BMI). Normal distribution of residuals from full models will be checked and, if needed, a transformation will be considered.

For binary variables, when we need to assess differences in frequencies, Chi-squares tests and Odds ratios (ORs) will be calculated. Multivariate logistic models will be considered to assess differences between

arms, adjusting for possible confounders. We will report nominal P-values and we will highlight associations that meet a false discovery rate adjusted P less than or equal to .05 by the Benjamini and Hochberg method.

Analyses on secondary endpoints will be considered as exploratory since we will not have enough power to draw definitive conclusions.

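### Centre, a randomisation stratum, is not named in any analysis model, the form of BMI is left open, and the baseline-adjusted ANCOVA is not ranked above the unadjusted t-test

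*Combined protocol and SAP*

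**What the plan says.** **Randomisation.** Section 13.2 says that "a stratified blocked randomization strategy will be used considering only the relevant prognostic factors". It names those factors: "Participants will be stratified according to center and BMI" (below 25 against 25 kg/m² or more), and uses fixed blocks of 6. On sites, Section 4.4 says: "This multicenter protocol will be conducted at the following five sites". That makes 5 × 2 = 10 strata.

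**Primary analysis.** Section 1.1 states the objective as "Non-inferiority of percent change in time of serum estradiol levels, adjusted for baseline levels". Section 13.4 then says: "Differences by arms of % change, change and final values will be tested considering t-test and ANCOVA models". On covariates it adds: "Estradiol at baseline will be included as explanatory variable together with other possible confounders such as BMI, age and time since last dose". The power paragraph of the same section sizes the trial "using a one-sided, two-sample t-test".

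**Elsewhere.** The secondary ANCOVAs in Section 13.5 give age and BMI as example confounders. Sections 13.6 and 13.8 define analysis sets and the handling of low values but add no covariates. Centre appears in none of these sections, and none says whether BMI enters as the randomised category or as a continuous variable.

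**The concern.** The plan calls centre and BMI prognostic when it randomises. If they are prognostic, stratified blocks remove their contribution from the true variance of the arm difference, but a model without them still counts that contribution as residual noise. The confidence interval is then a little wider than it needs to be.

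There is also a prespecification cost. With an open covariate list, two possible codings of BMI and two unranked tests, a reader cannot write down the single model that decides non-inferiority for each lower-frequency arm. Section 6.9 leaves the statistician unblinded to schedule, so it is worth settling the model on paper first.

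**Working it through.** **1. The plan's own figure.** Inputs from Section 13.4: 54 evaluable women per arm, SD 11, margin 6, true difference 0, one-sided level 0.025.
- SE = 11 × √(2/54) = 2.117.
- Noncentrality = 6/2.117 = 2.834 on 106 df.
- Noncentral-t power = 0.802 (0.794 with 53 per arm).
- Interval half-width = 1.983 × 2.117 = 4.20 points.
- 162/0.9 = 180 randomised.

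The stated sample size reproduces.

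**2. Degrees of freedom, two arms (108 women).** The t-test has 106. ANCOVA with baseline and BMI stratum has 108 − 4 = 104. Adding centre (4 df for five sites) leaves 100.

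**3. Gain from adding centre.** The documents give no R². Assume that the two strata explain 5%, 10% or 15% of the variance left after baseline, half each, and first that baseline explains none of the SD of 11.
- Without centre: power = E[Φ((6 − t₁₀₄ × SE × √(1 − R²_BMI) × √(χ²/104)) / (SE × √(1 − R²)))], averaged over χ² on 104 df.
- With centre: noncentral t on 100 df with SE × √(1 − R²).

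| Strata R² | Power, baseline + BMI | Power, plus centre | Gain (points) | Half-width |
|---|---|---|---|---|
| 0 | 0.8018 | 0.8015 | −0.03 | 4.20 to 4.20 |
| 5% | 0.8146 | 0.8212 | 0.65 | 4.145 to 4.094 |
| 10% | 0.8279 | 0.8411 | 1.32 | 4.092 to 3.984 |
| 15% | 0.8414 | 0.8609 | 1.95 | 4.038 to 3.872 |

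If centre holds 25% to 75% of the strata R², the gains become 0.3–1.0, 0.6–2.0 and 1.0–3.0 points.

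**4. If baseline estradiol explains variance.** Multiply SE² by 0.8 or 0.7 and repeat with the equal split. At 20% explained by baseline the gains are 0.45, 0.9 and 1.3 points; at 30% they are 0.3, 0.6 and 0.9.

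**5. Simulation.** 12,000 trials per R²; 180 women, blocks of 6 within 10 strata, 10% random dropout, baseline in both models. Centre shares of 35/20/15/15/15% and an even BMI split are assumed.
- Power without centre: 0.810, 0.819, 0.838.
- Power with centre: 0.814, 0.829, 0.856, so gains of 0.4, 1.0 and 1.8 points.
- At R² = 0: 0.793 against 0.790, a cost of 0.3 point.

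**6. Error rate.** One-sided size of the baseline + BMI model in closed form: 0.0236, 0.0221, 0.0205. A separate simulation of the unadjusted t-test (8,000 trials per setting) gave 0.023 at R² = 10% and 0.013 at 30%. All are below 0.025.

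**7. Time since last dose.** The Schema sets the final biomarker draw at 12 hours, 1.5–2.5 days and 5.5–6.5 days after the last active dose for arms 1, 2 and 3. Assume arm 1 fixed at 0.5 day and the other windows uniform (variance 1/12, so 1/24 averaged over two arms).
- Arm 2 v 1: between-arm variance (2 − 0.5)²/4 = 0.5625; share explained by arm 0.5625/(0.5625 + 0.0417) = 93%; SE multiplier 1/√(1 − 0.931) = 3.8.
- Arm 3 v 1: (6 − 0.5)²/4 = 7.5625; share 99.5%; SE multiplier about 13.5.

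This applies only if last dose means last active dose. Section 7.5 records the date and time of the last pill taken, and Section 5.2 has every woman take one tablet each evening at about 8 PM. On that reading the covariate is similar across arms and the collinearity disappears.

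**The case against.** The best defence is that the documents already lean to an adjusted analysis. Section 1.1 asks for adjustment for baseline, Section 13.4 makes baseline estradiol mandatory and lists BMI first among further covariates, and the t-test in the power paragraph is a sizing device, conservative when the final analysis is adjusted. The covariate list is open, so centre is unnamed rather than excluded. All of that stands. It narrows the gap to one missing covariate, the coding of BMI and the missing ranking, but does not close it.

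It is also fair that the benefit rests on R² values that the documents do not supply. Sections 8.1 and 10.1 send the primary estradiol measurement to one laboratory, which limits any centre effect. Section 13.4 expects many final values below detection, and Section 9.1 assigns these half the limit. For those women percentage change depends on baseline alone, so baseline may absorb much of the variance (Section 13.6 considers another method for such values).

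A reader might infer that ignoring the strata risks a false claim of non-inferiority, or that the trial is undersized. The check shows the opposite direction of error, and 54 per arm stands. A reader might also infer a power loss of 2.5 to 8 points. That compares a bare t-test with a model holding both strata at an R² of 10% to 30%, whereas the plan already names baseline and BMI. Nor do the documents show that time since last dose would wreck the primary model, since its meaning is not defined.

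**Conclusion.** The point holds as an optional, low-cost improvement. That centre is absent from the analysis sections, that the form of BMI is open and that the two tests are unranked is certain from the text. The material benefit is not. Adding centre is worth about 0.3 to 2 power points if the strata explain 5% to 15% of the variance in equal parts, towards the lower end if baseline estradiol explains 20% to 30%. It could reach 3 points only at 15% with most of that belonging to centre and none to baseline, and it could be near zero. If the strata explain nothing, including centre costs 0.03 point in closed form and 0.3 in simulation. Neither the error rate nor the sample size is in question.

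**What to change.** In Section 13.4, name one primary model for each of the two comparisons: ANCOVA of percentage change in estradiol on arm, baseline estradiol, BMI stratum as randomised, and centre. State how very small centres will be pooled. The threshold is the trial team's choice; fewer than 12 randomised women, one block of 6 in each BMI stratum, is one example. Fix it before unblinding and, given Section 6.9, before the estradiol results are available to the statistician.

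Make the t-test supportive. Put age and time since last dose in sensitivity models, and state whether last dose means the last active dose or the last tablet. Continuous BMI is also defensible and can be a sensitivity model; what matters is that the primary form is stated. Adding the strata to the secondary ANCOVAs in Section 13.5 is optional, since the plan calls those analyses exploratory.

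The cost is a few sentences and no new data or participants. The strata use 5 df (4 for centre, 1 for BMI), leaving 100 residual df per comparison.
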